Randomization assignments will be performed by the CC via the National Dental PBRN practitioner database. The RAS staff will notify the practitioners on their randomization assignment. Randomization assignments will be stratified by region; therefore, each region will receive the devices prior to the start of the study. Once the RAS staff receives notification of the practitioner's randomization assignment, the practitioner will receive the device (if assigned to arm) from the RAS.

Following device familiarization if randomized to a device arm, practitioners will participate in the intervention period. We anticipate the intervention period to take approximately eight weeks per practitioner to train on the devices and enroll/complete 20 patients each with one lesion. Our previous study had shown that practitioners, on average, enrolled 19 patients per month. Each patient's (subject's) participation will be limited to the duration of the dental visit. The patient will undergo further caries detection using a device if in a device arm, and data collection and recording procedures will be performed. Practitioners randomized to the no device arm will begin the intervention stage after having received their randomization assignments.

Following the intervention phase, practitioners will complete a post-study vignette with scenarios and clinical photos. This will be completed online. For those assigned to a device arm, practitioners will also complete a post-study questionnaire on how they "self-trained" on the device, resources utilized for device familiarization, and utility of the device. For those not assigned to a device arm, practitioners will complete a post-study questionnaire on the vignette and participation in the study.

Pilot Testing

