11.2 Sample Size Considerations

Power to detect differences between each of the device groups and the no-device group was approximated based on two-sided testing with the Chi-square statistic, with adjustments for multiple comparisons and for the effect of clustering within practitioner. A Bonferroni-type adjustment was used to account for two comparisons: no device versus each of the device groups. This approach yields somewhat conservative estimates of power, since the two device-versus-control comparisons are pre-planned, and will each be conducted at the 95% confidence level in the statistical analysis of the actual study data, as described in the following section.

The unit of randomization is the individual practitioner. The effect of cluster randomization was taken into account in the calculation of study power and sample size requirements by adjusting the total sample size using the design effect, calculated as $1 + (m - 1)\rho$, where m = the average number of lesions per practitioner and $\rho =$ the intraclass correlation coefficient (ICC). The effective sample size was calculated by dividing the total sample size by the design effect. The effective sample size is the number of observations which would be required to achieve the same power, using an independently-randomized design, as the cluster-randomized design with the given total sample size. Power and detectable difference estimates were then calculated for the chi-square statistic using the effective sample sizes for values of ICC from 0.0 to 0.05.

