Two outcomes are of interest: the proportion of all SOCL that are opened and the proportion of opened SOCL that are carious. Practitioners will each contribute 20 lesions to the study during the intervention period. The planned recruitment of 30 practitioners per group yields a total sample size of 600 lesions per group for the first outcome. The total sample size for the second outcome will be the number of lesions that are opened. Because the study design does not include follow-up of individual patients, patient-level dropout is not anticipated to be a major consideration. Drop-out of practitioners is possible, and could cause the loss of multiple observations, depending on the number of patients that are accrued prior to the practitioner drop-out, up to a maximum of 30. Part of the intent of the pre-intervention run-in period is to identify practitioners who are not likely to succeed in recruiting the required number of patients, and to provide an opportunity for practitioners to drop out prior to randomization, so that they can be replaced without interference to the randomization process. Still, it is possible that practitioners might drop out after randomization. Anticipating a severe situation in which 10% of the initial 30 practitioners in each group drop out prior to contributing any data, power and detectable difference calculations were repeated for 27 practitioners per group, and a total sample size of 540 lesions per group. While this is an extreme and unlikely occurrence, the additional tables provide an indication of the effect of a substantial loss of data.

The expected rates of lesion opening are 50% for no device and 30-35% for the device groups. Differences in rates of opening that would be detectable with 80% power are as follows:

Difference detectable with 80% power				ICC		
	0.00	0.01	0.02	0.03	0.04	0.05
Effective						
sample/group:	600	504	435	382	341	308
Detectable difference						
(%):	9.1	9.9	10.7	11.4	12.0	12.7
Rate in device group						
(%):	40.8	40.1	39.3	38.6	38.0	37.3

Assuming loss of 10% of practitioners per group, without contributing any data to the study:

Difference detectable with 80% power	ICC							
	0 0.01 0.02 0.03 0.04 0.0							
Effective comple/groups	E 40	454	204	244	207	077		
Effective sample/group:	540	454	391	344	307	211		
Detectable difference (%):	9.6	10.4	11.3	12.0	12.7	13.4		
Rate in device group (%):	40.4	39.6	38.7	38.0	37.3	36.6		

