11.3 Final Analysis Plan

This is the planned analysis based on the data we plan to collect. An appropriate statistical model must take into account both the level of measurement of the outcome variables and the study design. Both of the primary outcome variables, surgical treatment of the lesion and extension into dentin, may be appropriately represented as dichotomous variables. Each practitioner will be randomized to use a single device, or no device and no a priori study design levels defined within the level of practitioner. This approach yields a two-level hierarchical study design. A characteristic of this two-level model is the presence of correlation among the multiple observations obtained from each practitioner. The primary analysis framework will be based on mixed-model logistic regression analysis, implemented with generalized estimating equations (GEE), accounting for correlation among the clusters of observations made by the same practitioners. These models will include a term representing the individual practitioner as a random effect and study arm as a fixed effect. Additional control variables, including region, may be included if it is found that these are needed to account for possibly different distributions of practitioner or patient characteristics. Details of the analysis approach and related considerations are provided in Appendix E

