For evaluation of differences in proportions of lesions treated operatively among the intervention groups, the analysis data set will include all SOCLs that are enrolled by the study practitioners. The outcome variable for this analysis will be a dichotomous variable indicating whether the SOCL was treated operatively. Proportions of SOCL treated operatively will be calculated for each study arm. Confidence intervals, adjusted for correlation within clusters (practitioners), will be estimated from the GEE models. Statistical tests for differences in proportions among the three study arms will be based on Type III tests from the GEE analysis, controlling for the effect of clustering by practitioner. An indicator variable representing the study arm will be included as a fixed effect in this model, and a term representing the individual practitioners will be included as a random effect. The effect of regional site will be evaluated as a fixed effect, and will be included in the model if it explains a statistically significant portion of the observed variation in the outcome variable. The two pre-planned comparisons of the device versus no-device arms will be evaluated using contrasts, and will be tested using Chi-square tests of score statistics. Because these are pre-planned comparisons, each of these tests will be conducted at the 95% confidence level, using per-comparison error rates.

For the comparison of proportions of lesions treated operatively that have caries extending into dentin, the analysis data set will include all SOCLs that were treated operatively by the study practitioners. The outcome variable will be a dichotomous variable indicating whether the lesion extended into the dentin. The analysis will be identical to that utilized for Aim 1, except for the reduced analytic sample. GEE-based mixed-model logistic regression will be used to estimate confidence intervals for proportions of SOCLs extending into dentin, controlling for clustering by

practitioner and, if needed, for regional differences. Two pre-planned comparisons will be conducted using contrasts to compare each of the device study arms with the no-device arm.

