The analysis data set for identification of clinical characteristics of SOCLs that predict caries extending into the dentin will include all SOCLs that were treated operatively by the study practitioners. The outcome variable will be a dichotomous variable indicating whether the lesion extended into the dentin. The primary statistical model will be mixed-model logistic regression, implemented with GEE in order to account for clustered observations. Clinical characteristics that will be evaluated as potential predictors of caries extending into dentin are luster, color, roughness on examination with explorer, tooth position (molar or premolar), and patient dental history variables. A term representing the individual practitioner will be included in the model as a random effect. Study arm, region and terms representing each of the clinical characteristics of the lesions will be included as fixed effects. Initial analyses will be conducted considering each of the clinical characteristic variables singly, along with region and the random effect term, to determine whether there is a significant "univariate" association between the potential predictor and the outcome. Following this series of analyses, a multi-variable approach will be used to evaluate the joint association between the clinical characteristics and the outcome. This analysis will include the practitioner term as a random effect, region, and all of the clinical characteristics that were associated with dentin involvement, at p < 0.10, in the "univariate" analyses. The liberal significance level, using p < 0.10, will be used in order to allow for the possibility that some variables may become more significant in the multivariable approach than in the "univariate" analyses. Further analysis may be conducted, in which non-significant predictors are removed from the multivariable model in order to obtain a more concise prediction model.

Additional descriptive analyses will be conducted to evaluate possible association of practitioner and patient characteristics with outcome measures or other study variables. Depending on the specific structures of these auxiliary analyses, appropriate analysis models may include hierarchical methods, or single-level approaches such as contingency table analysis using the Chi-square statistic or ordinary analysis of variance or logistic regression analyses.

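### Region stratifies the randomisation but enters both primary models only conditionally; it should be a fixed effect in each, although the numerical consequence is small

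*Protocol*

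**What the plan says.** Section 4 of the protocol: "Randomization assignments will be stratified by region". Section 11.2: "The unit of randomization is the individual practitioner". Section 5.2 plans 90 practitioners, about 15 in each of six regions, which is about five per arm within a region.

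The protocol then treats region in four ways:

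- **Operative treatment (Appendix E).** Regional site is first assessed, and its place in the model is conditional: it "will be included in the model if it explains a statistically significant portion of the observed variation in the outcome variable". No significance level is given for that test.
- **Dentin extension (Appendix E).** The model controls for "practitioner and, if needed, for regional differences".
- **Primary analysis framework (section 11.3).** "Additional control variables, including region, may be included if it is found that these are needed to account for possibly different distributions". The distributions meant are those of patients' and practitioners' features, so this is a criterion of imbalance, not of association with the outcome.
- **Secondary predictor model (Appendix E).** "Study arm, region and terms representing each of the clinical characteristics of the lesions will be included as fixed effects".

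No section makes region a fixed part of the primary model for either primary outcome.

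**The concern.** Stratifying by region balances the arms within region, so between-region variation drops out of the difference between arms. A model without region still counts that variation as error. Its standard errors are then too large for the design, and its tests are conservative.

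The rule also leaves the primary model undecided until the outcome data have been examined, and section 15.4 foresees no masking. The two primary outcomes could end up with different models. The entry criteria in section 11.3 and Appendix E could also point in different directions for the same data. The stratification factor is compulsory in a secondary model and optional in the primary ones, which is the wrong way round.

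At stake is mainly a primary model that is fixed in advance and matches the design. Whether accuracy or power is also at stake is checked below.

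**Working it through.** **The plan's own power figure.** "The planned recruitment of 30 practitioners per group yields a total sample size of 600 lesions per group for the first outcome". At ICC 0.05 the design effect is 1 + 19 × 0.05 = 1.95, and the effective size is 600 / 1.95 = 308 per arm. For 50% versus 35% at a two-sided alpha of 0.025, power is 93.8%, or 92.8% with continuity correction. Section 11.2 states about 92%, so the figure reproduces. It takes no account of region, and this point does not change it.

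**Inputs.** Six regions × three arms × five practitioners, 20 lesions each, ICC 0.05 (the top of the protocol's range). Two assumptions: region accounts for a share *s* of between-practitioner variance, taken from 10% to 50%, and the significance rule uses the 5% level. Practitioner means are analysed with a linear model.

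**How often the rule keeps region.** In units of p(1−p), the region variance is R = s × 0.05. The remaining variance of a practitioner mean is W = (1−s) × 0.05 + 0.95/20. The F statistic for region is distributed as (1 + 15R/W) times F(5, 82), with critical value 2.326.

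**What omitting region in every trial would do.** The expected error mean square rises from W to W + (75/87)R, so the SE is multiplied by √(1 + (75/87)R/W).

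| Share s | R | W | 1 + 15R/W | Region kept | SE ratio if never included |
|---|---|---|---|---|---|
| 10% | 0.005 | 0.0925 | 1.81 | 28% | 1.02 |
| 20% | 0.010 | 0.0875 | 2.71 | 51% | 1.05 |
| 30% | 0.015 | 0.0825 | 3.73 | 68% | 1.08 |
| 50% | 0.025 | 0.0725 | 6.17 | 86% | 1.14 |

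The nominal 5% test would then run at 2[1 − Φ(1.96 × 1.048)] = 4.0% for a 20% share and 2[1 − Φ(1.96 × 1.139)] = 2.6% for a 50% share. Simulation gave 3.9% and 2.8%.

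**Dentin extension.** Section 11.2 expects 300 and 210 opened lesions per arm, or 10 and 7 per practitioner. The mean of 1/m over the three arms is (1/10 + 1/7 + 1/7)/3 = 0.129, so at a 20% share W = 0.040 + 0.95 × 0.129 = 0.162 and 1 + 15R/W = 1.93. Region is kept in about 31% of trials, and in about 66% at a 50% share.

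**What the stated rule does** (simulation, ICC 0.05, 20,000 replicates).

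- Type I error is 4.7% to 5.1% for region shares from 0 to 50%.
- In trials where the test drops region, the SE is only about 1% to 1.5% above the region-adjusted SE, because those are the trials in which the observed region differences are small. Type I error in them is about 4.0% to 5.1%.
- The decision on an arm differs from that under always adjusting in at most about 0.6% of trials, and power is within about 0.4 point.

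A separate beta-binomial simulation, with ICC 0.05 within region, alpha 0.05 and 50% versus 40% opened, gave:

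| SD between regions (assumed) | Region kept | Power: always | Power: stated rule | Power: never |
|---|---|---|---|---|
| 5 points | 48% | 69.4% | 69.0% | 66.2% |
| 10 points | 90% | 71.1% | 71.0% | 58.6% |

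**Check with logistic GEE** (400 null runs, robust Wald tests). At region SDs of 0, 5 and 10 points, the SE with region was 0.97, 0.94 and 0.87 of that without. Rejection rates were 9.0%, 6.8% and 5.2% under the rule, against 9.0%, 7.0% and 5.5% with region always in. The rule tracks always adjusting here too. At SD 0 the excess over 5% also appears without region (8.2%), so it does not come from the selection step. Monte Carlo error is 1 to 1.5 points, and the protocol names score tests rather than Wald tests.

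**The case against.** The strongest reply is that the protocol does not ignore region. It tests region and keeps it when it matters, and the simulations show that this recovers nearly everything that always adjusting would give. That stands, and it limits the size of the point.

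A reader might infer from the stratified design that intervals will be 5% to 14% too wide, or that the 5% test will run at about 4% to 3%. The documents do not support that reading, because those figures describe a model that never includes region. The same holds for a dramatic power loss. At ICC 0.20 and a 30% share, power for 15 points is about 70% if region is never included. It is 78.3% under the stated rule and 78.4% if region is always included. That ICC is also four times the protocol's upper value.

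A reader might also infer that the rule lets the team steer towards a favourable result. The Appendix E test concerns region and the outcome, not the arm effect, and the arms are balanced within region by design. The scope for steering is small, and no inflation of type I error from the rule was seen.

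Nor should the protocol be faulted for lacking a complete covariate list, which can properly be left to a statistical analysis plan. The same defence does not cover region: here the protocol states a selection rule, and a later plan that followed Appendix E would inherit it.

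**Conclusion.** The point holds as a minor one. The protocol stratifies by region, makes region conditional in both primary models under criteria that disagree, and includes it without condition in a secondary model. With a moderate region effect, whether the operative-treatment model contains the stratification factor is close to a coin toss. For dentin extension, at the same 20% share, it would be left out in about two trials in three.

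This is a mismatch between design and analysis and a weakness of pre-specification. It is not a demonstrated bias: under the stated rule type I error stays near 5% and power is within about half a point of always adjusting. These sizes rest on assumed region effects, a 5% level for the region test, ICC 0.05 and practitioner-level linear models, with only a small GEE check. The inconsistency in the text depends on none of these assumptions.

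**What to change.** In Appendix E, delete the condition that region must be statistically significant, and delete the if-needed condition for dentin extension. State there and in section 11.3 that region is included as a fixed effect in the primary model for both outcomes, whatever its p-value, and take region out of the section 11.3 sentence on optional control variables. This brings the primary models into line with the secondary predictor model.

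The cost is about one sentence in each place and five degrees of freedom out of 90 practitioners. The sample size does not change.

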4 STUDY DESIGN

The study combines elements of a pre-and post-control group design and a randomized clinical trial. To achieve a sample of 1200 lesions for each of the three arms in the full study, we wish to enroll a total of 90 practitioners (total from all six regions) in the study, each of whom will enroll approximately 40 SOCLs (one lesion/patient), 20 enrolled/completed lesions during the pre-intervention phase, and 20 enrolled/completed lesions during the intervention phase. Thus, the patients enrolled will be representative of the patients with such lesions in the practitioners' offices.

Overview of Study Schedule

There will be a 4-8 month window for practitioner enrollment. When a practitioner has completed the study pre-enrollment requirements and the region has IRB approval s/he will be ready to begin the study. Following enrollment, as part of their study training, practitioners will be trained as follows:

- 1. Study Procedure Training: RCs will provide study procedure training, and practitioners will also receive a training manual which will serve as a reference and will highlight important information.
- 2. Standardization Training Pertaining to SOCLs: During the Study Procedure Training with the practitioner, the RC will provide photographs of teeth with SOCLs and review the clinical characteristics of SOCLs. The RC will answer any questions the practitioner might have about these characteristics. The photographs will be given to the practitioners to place in the operatory for review as needed.
- 3. Device Delivery and Set Up: Practitioners randomized to the device arm following the pre-intervention data collection phase will receive the devices from the RAS, and the RAS will assist with device set up.

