For evaluation of differences in proportions of lesions treated operatively among the intervention groups, the analysis data set will include all SOCLs that are enrolled by the study practitioners. The outcome variable for this analysis will be a dichotomous variable indicating whether the SOCL was treated operatively.

For the comparison of proportions of lesions treated operatively that have caries extending into dentin, the analysis data set will include all SOCLs that were treated operatively by the study practitioners. The outcome variable will be a dichotomous variable indicating whether the lesion extended into the dentin.

Exploratory statistical analyses will be conducted to examine changes in practitioners' rates of operative treatment of lesions during the pre-randomization run-in period versus their rates during the post-randomization intervention period. Further analyses will be conducted to evaluate possible associations between pre- to post-randomization changes in practitioners' rates of operative treatment and variables representing practitioners' perception of changes in the decision-making process. This analysis will be conducted using the practitioner as the unit of analysis, and will utilize a mixed-model analysis of variance approach to evaluate changes in rates and to compare mean changes among the intervention groups, accounting for repeated observations for the practitioners.

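### The exploratory run-in versus intervention comparison of arms uses raw changes in practitioner rates, which is unbiased but less precise than adjusting for the run-in rate

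*Protocol*

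**What the plan says.** Section 4 of the protocol has each practitioner contribute "20 enrolled/completed lesions during the pre-intervention phase, and 20 enrolled/completed lesions during the intervention phase", with randomization after the first of these periods.

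The last paragraph of Appendix E plans exploratory analyses of practitioners' operative-treatment rates in the run-in against their rates after randomization. The practitioner is the unit, and the analysis "will utilize a mixed-model analysis of variance approach to evaluate changes in rates and to compare mean changes among the intervention groups", with allowance for repeated observations on each practitioner. The same paragraph adds: "Further analyses will be conducted to evaluate possible associations between pre- to post-randomization changes in" those rates and practitioners' perceptions of how their decision-making changed. The run-in rate is not named as a covariate. Section 11.3 announces the same exploratory analyses without fixing the method.

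The confirmatory arm comparisons are separate. They are the GEE contrasts of each device arm with the no-device arm, set out earlier in Appendix E. The sample size in Section 11.2 was worked out "using the effective sample sizes for values of ICC from 0.0 to 0.05".

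**The concern.** A practitioner's rate on 20 lesions carries a large binomial error. Subtracting the run-in rate removes the stable difference between practitioners but brings in a second binomial error. That trade pays only if stable differences make up at least half of the variance of an observed rate. At the ICCs the protocol works with, they mostly do not.

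The run-in supplies half of each practitioner's lesions, 20 of 40, and this is the arm comparison that the protocol builds on the run-in rates. If it rests on raw changes, a difference between arms may look inconclusive when the same data, adjusted for the run-in rate, would show it more clearly.

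**Working it through.** **Inputs.** The number of lesions per practitioner per period is m = 20 (Section 4). Section 11.2 gives the number of practitioners: "The planned recruitment of 30 practitioners per group yields a total sample size of 600 lesions per group for the first outcome". The ICC range is 0 to 0.05 (Section 11.2). The expected rates are 50% without a device and 30-35% with one (Section 11.2). The protocol states no significance level for this exploratory analysis, so I use two-sided 5% per comparison, as in the primary contrasts.

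**The plan's own figures first.** Section 11.2 states: "The effective sample size was calculated by dividing the total sample size by the design effect". With 600/(1 + 19 x ICC), the results for ICC 0 to 0.05 are 600, 504, 435, 382, 341 and 308, exactly as tabulated. The detectable differences, with a continuity-corrected test at 0.025, come to 9.0, 9.9, 10.6, 11.3, 12.0 and 12.7 points. The protocol gives 9.1, 9.9, 10.7, 11.4, 12.0 and 12.7. It gives no figure for the change analysis.

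**Assumption.** The protocol states no correlation between periods. I assume that each practitioner's tendency is the same in both periods, which is the case most favourable to change scores.

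**Formulas.**
- Variance of a practitioner's rate at 50%: v = 0.25 x (1 + 19 x ICC)/20.
- Correlation between a practitioner's two rates: r = 20 x ICC/(1 + 19 x ICC).
- Variance relative to intervention-period rates alone: 2(1 - r) for change and 1 - r² for baseline adjustment. Their ratio is 2/(1 + r).
- SE of an arm difference: square root of (2 x v x factor/30).

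Example at ICC 0.05: v = 0.25 x 1.95/20 = 0.0244 and r = 1/1.95 = 0.51. The factors are 0.97 for change and 0.74 for adjustment, giving SEs of 3.98 and 3.46 points.

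| ICC | r | SE, change | SE, adjusted | SE, intervention only | Variance, change / adjusted | Variance, change / intervention only | Power at 10 points, change | Power at 10 points, adjusted |
|---|---|---|---|---|---|---|---|---|
| 0.01 | 0.17 | 4.06 | 3.10 | 3.15 | 1.71 | 1.66 | 69% | 90% |
| 0.02 | 0.29 | 4.04 | 3.25 | 3.39 | 1.55 | 1.42 | 70% | 87% |
| 0.03 | 0.38 | 4.02 | 3.34 | 3.62 | 1.45 | 1.24 | 70% | 85% |
| 0.04 | 0.45 | 4.00 | 3.41 | 3.83 | 1.38 | 1.09 | 71% | 83% |
| 0.05 | 0.51 | 3.98 | 3.46 | 4.03 | 1.32 | 0.97 | 71% | 82% |

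SEs are in percentage points. At ICC 0 the variance ratio of change to adjusted is 2.00.

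**Break-even with ignoring the run-in.** Change beats intervention-only rates when 2(1 - r) < 1, that is r > 0.5. Setting 20 x ICC = 0.5 x (1 + 19 x ICC) gives ICC = 0.5/10.5 = 0.048.

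**At the expected effect.** For 50% versus 35%, power is about 96% with change and 99% or more with adjustment.

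**Sensitivity.** If only 80% of the practitioner variance is shared between periods, the ratio at ICC 0.05 rises from 1.32 to 1.42. At an ICC well above the protocol's range the penalty fades: at 0.20, r = 4/4.8 = 0.83 and the ratio is 2/1.83 = 1.09.

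**Simulation.** Beta-binomial data gave SEs for change and adjusted of 4.04 and 3.23 at ICC 0.02, and 3.96 and 3.48 at ICC 0.05. Both estimators were unbiased.

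**The case against.** **It is exploratory and costs only precision.** This stands. The run-in precedes randomization, so both comparisons are unbiased. No primary test or stated power depends on this one. The 10-point difference is my choice, although it lies within the 9.1 to 12.7 points that the protocol tabulates as detectable. At the effect the protocol expects, little power is lost.

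**The mixed model may already deal with it.** Appendix E allows for repeated observations, and a two-period model that constrains the run-in means to be equal across arms would recover the adjusted precision. The text does not exclude that constraint, and an analysis plan could add it. But what the text names is a comparison of mean changes. With one rate per practitioner per period, the unconstrained arm-by-period contrast is that same change-score comparison, so allowing for repeated observations does not by itself help.

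**A stronger reading that does not hold.** A reader might infer that regression to the mean contaminates the perception analysis, because with no true change the observed change correlates -0.64 to -0.49 with the observed run-in rate (ICC 0.01 to 0.05). Write the two observed rates as T + e1 and T + e2, where T is the practitioner's true tendency. The change is then e2 - e1, which is uncorrelated with T. A perception variable related to T therefore has zero expected correlation with the change. The negative correlation runs through the chance error e1 alone, and nothing in the protocol suggests that perceptions track that error.

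Adjusting the perception analysis for the run-in rate could do harm, because r is also the reliability of that rate, only 0.17 to 0.51. Take a variable that is related to T only and correlates 0.30 with the run-in rate. Its partial correlation with the intervention rate given the run-in rate is 0.30(1 - r)/√[(1 - 0.09)(1 - r²)]. That is 0.27 at ICC 0.01, 0.23 at 0.02 and 0.18 at 0.05, with no true change at all.

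**Conclusion.** The point holds for the arm comparison only. The planned comparison of mean changes is valid but inefficient, with 1.71 to 1.32 times the variance of a baseline-adjusted comparison for ICC 0.01 to 0.05. Below about 0.048 it does worse than leaving the run-in out.

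The absolute SEs and powers rest on 30 practitioners per arm, 20 lesions per period and rates near 50%. The variance ratio does not depend on the 50% rate. All of these figures assume a tendency that persists fully between periods, and less persistence makes change scores look worse.

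The consequence is modest: a weaker exploratory result for differences around 10 points, and little loss at the expected 15. The documents support no claim of bias in the arm comparison, no effect on the primary GEE analyses or the sample size, and no fault in relating perceptions to change scores.

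**What to change.** In the last paragraph of Appendix E, and in the matching text of Section 11.3, replace the comparison of mean changes among arms with one of the following:

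- a comparison of intervention-period practitioner rates among arms, with the practitioner's run-in rate as a covariate; or
- a two-period mixed model that gives all arms a common pre-randomization mean.

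Report the raw changes by arm descriptively. Leave the perception analysis on change scores.

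The cost is a few words of analysis text. The run-in rates are already collected, and no patient, visit or procedure is added.
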